1.1.2. IOP measurement methods

To provide more reliable data, twenty-four hour diurnal tension curves (DTC) can be measured. However, 24-hour IOP monitoring is unfeasible and time consuming in the majority of circumstances. The modified diurnal tension curve (mDTC) involving IOP measurements every 2 or 3 hours during office hours is therefore often used as a shorter alternative.

The water drinking test (WDT) is a tool that aims to indirectly evaluate the eye's aqueous humor outflow facility^{[8] [9]} by putting the drainage system under 'stress' in a test similar to that which may be used in cardiology or endocrinology. More recent research has suggested that water overload with the WDT may correlate well with the IOP peaks detected during a 24-hour intraocular pressure measure^[10].

It remains unclear as to the physiological mechanism behind this observed IOP rise. Several hypotheses exist including increases in outflow resistance^[11], episcleral venous pressure^[12], choroidal expansion^[13] and change in blood osmolality. However, it has been observed in one study that 20% of subjects developed change in IOP before change in osmolality could be detected.

Centrally mediated causes, possibly triggered by gastric expansion have been postulated with regards to activation of the autonomic nervous system^[14], but this has mainly been characterised in terms of cardiovascular physiology as oppose to intraocular pressure rise. Some evidence has been published to suggest the time course of the autonomic changes observed (rise in blood pressure, reduction in heart rate) are not consistent with reflex activity^[15], however in this study only 500mls of water was ingested over 3-4 minutes. This aspect of the test requires further characterisation in relation to the time profiles of the IOP rise.

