1.2 RATIONALE FOR CURRENT STUDY

The current method of using the mDTC is time consuming, labour intensive, and incomprehensive. Not only does the WDT have the potential to improve upon the time consuming and labour intensive nature of the test, but given the active element may improve diagnostic pickup and sensitivity for disease progression, given that the mDTC is only feasibly conducted during office hours.

Further work comparing the currently used mDTC and the WDT to assess IOP peak and fluctuation is necessary. The study mentioned above^[24] showed strong evidence of the clinical applicability of the WDT and its correlation with the mDTC. Furthermore, the IOP peak obtained by the WDT has been proved to be an independent risk factor for the development and progression of glaucoma^[5,8]. However, to date, there are no studies focusing on OCT data that will indicate progression of 'pre-perimetric' glaucoma, or any studies focusing on the most commonly referred group of patients referred for the test. This will aid us to discern the best way to assess IOP peaks and manage glaucoma treatment and progression.

Our hypotheses are:

- The peak IOP during the WDT correlates with mDCT
- Peak IOP during the WDT is associated with rate of glaucoma progression as measured with OCT
- Changes in autonomic variables associated with IOP rise are consistent with a autonomic reflex as the physiological mechanism behind the test.

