2. STUDY OBJECTIVES

- **Primary research objective** is to investigate the correlation and agreement between the intraocular pressure peaks detected during the water drinking test and the standard phasing test.

Secondary research objective is to correlate the IOPs obtained with both tests and prognostic outcome of the patients enrolled in the study to see whether these methods have predictive value for glaucoma progression. We will also measure autonomic nervous system activation (pupil size, heart rate and postural BP) during the test to investigate one possible mechanism behind it.

Lay summary

Raised intraocular pressure (IOP) is the main risk factor for the development and progression of glaucoma. The mDTC is a test that consists of four to five eye pressure measurements taken throughout office hours to check for rises in pressure that may be missed during their clinic appointment. To better try to assess the IOP peaks in a more time-efficient way, the water-drinking test has been developed. This involves the patient drinking a weight-adjusted volume of water within 5 minutes which has the effect of testing the ability to cope with increased demand for fluid to leave the eye. It is unclear as to the physiological mechanism by which this occurs. In this study we aim to compare the eye pressure measurements with both tests, and to see if either have any bearing on whether the patient's disease is getting worse. We also aim to show the changes in blood pressure and heart rate throughout the test.

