3.1 STUDY OUTCOME MEASURES

- **Primary outcome measure:**

Intraocular pressures measured during the mDTC
Intraocular pressures measured during the WDT

- **Secondary outcome measures:** postural blood pressure, heart rate, pupil diameter, pulse oximetry, OCT imaging parameters (angiography and anterior segment angle size) including current and future rates of progression using nerve fibre layer thickness on optical coherence tomography (OCT) and visual field testing.

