3.1.2. Interventions

Baseline and qualification assessments will take place on the day of the study. These include a medical, ophthalmic and drug history, ophthalmic examination, postural blood pressure measurement, testing of visual acuity, OCT/OCTA of the optic disc and macula and then IOP assessment. All ophthalmic assessments will be done on both eyes using the Heidelberg Spectralis® imaging system. The mDTC will be conducted as part of patient's regular visit and is standard of care which consists of 5 IOP measurements beginning at 8am and 2 hourly afterwards (+/- 15min). Following completion of mDTC patients will have their WDT as detailed below.

The water drinking test will occur following the mDTC and will involve the patient drinking 800mL of water at room temperature, within a maximum of five minutes, after a period of no fluid intake of at least 2 hours. This will come after a period of no fluid intake of at least 2 hours (2pm onwards). For the WDT, the first IOP measure will correspond to the last mDTC measure, and three IOP measurements will be made after water intake with a 15-minute interval between each. IOP measurements will be recorded using Goldmann Applanation Tonometry (GAT). At each 15 minute interval, postural blood pressure, heart rate, oxygen saturations and pupil diameter will be measured. The ambient light conditions will be monitored with a light meter. Imaging will then be repeated after one hour of the test.

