7.4.3 Statistical analysis

No interim analyses will take place as part of this pilot study. Data will be acquired using integrated Heidelberg® software packaged with the Heidelberg® Spectralis OCT system. Data for this initial pilot study will be collected using Microsoft® Excel, and analysed using R and GraphPad prism to compare IOPs between the mDCT and WDT.

Specific analyses will include:

- Generation of baseline data including mean and standard deviation of baseline characteristics
- Bland-Altman agreement analysis of the primary outcome
- Correlation analysis between WDT and rate of progression.
- Analysis of change in OCT measurements
- Change over time analysis for secondary outcomes compared to baseline

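### No pre-specified analysis links the autonomic variables to the IOP rise that hypothesis 3 is about

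*Combined protocol and SAP*

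**What the plan says.** Section 1.2 (Rationale for current study) states the third hypothesis as: "Changes in autonomic variables associated with IOP rise are consistent with a autonomic reflex as the physiological mechanism behind the test". Section 1.1.2 (IOP measurement methods) gives the reason. It cites earlier evidence that the time course of the autonomic changes did not fit reflex activity, and then says: "This aspect of the test requires further characterisation in relation to the time profiles of the IOP rise". Section 2 (Study objectives) places the autonomic measurements under the secondary objective, "during the test to investigate one possible mechanism behind it".

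Section 3.1 (Study outcome measures) lists "postural blood pressure, heart rate, pupil diameter, pulse oximetry" among the secondary outcomes. It lists "Intraocular pressures measured during the WDT" as a primary outcome.

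Section 3.1.2 (Interventions) takes the last reading of the modified diurnal tension curve as the starting IOP, after which "three IOP measurements will be made after water intake with a 15-minute interval between each". The autonomic variables are read at the same 15-minute intervals.

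Section 7.4.3 (Statistical analysis) names five analyses. The one that reaches the autonomic variables is "Change over time analysis for secondary outcomes compared to baseline". The only correlation in the list relates the water drinking test to rate of progression, which serves hypothesis 2.

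**The concern.** The hypothesis is about a relation between two sets of readings, and the listed analysis looks at one set. A change-from-baseline comparison asks whether a variable moves after water. Autonomic variables and IOP can both move because every participant drinks the water, without the patients who show the autonomic change being those who show the IOP rise, and without one change preceding the other.

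Two things are at stake. Followed as listed, the plan yields no estimate of the relation named in the hypothesis. If a linking analysis is instead chosen once the data are in hand, there are four autonomic variables and more than one possible lag to choose from, and the plan names neither a lead variable nor a result that would count as consistent with a reflex.

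**Working it through.** The plan gives no figure for hypothesis 3, so there is none to reproduce. Its one calculation (section 7.1) concerns a 2 mmHg difference in IOP peak with SD 2 mmHg. Only the resulting 40 patients are used below.

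**Step 1. Which listed analysis contains both IOP and an autonomic variable?**

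| Analysis in 7.4.3 | IOP response to water | Autonomic response to water |
|---|---|---|
| Baseline summaries | no | no |
| Bland-Altman on the primary outcome | yes | no |
| Correlation of water drinking test with progression | yes | no |
| Change in OCT measurements | no | no |
| Change over time in secondary outcomes | no | yes |

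No row contains both.

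**Step 2. What do change-from-baseline tests say about association?** The simulation used 40 patients, 20,000 runs, and one IOP change and one autonomic change per patient. Both were normal with a mean of 0.8 SD, tested two-sided at 5%. The 0.8 SD and the correlations are assumptions, since the documents give none.

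| True correlation | Both change tests significant | Correlation test significant |
|---|---|---|
| 0 | about 99.7% | 4.9% |
| 0.5 | about 99.7% | 92.6% |
| 0.9 | about 99.7% | 100% |
| -0.5 | about 99.7% | 92.5% |

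The middle column does not move. This follows from how the tests are built; the table only shows the extent.

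**Step 3. What could the planned data detect?** For a correlation with one value per patient, two-sided 5% and 80% power, the Fisher z approximation gives

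r = tanh(2.80 / sqrt(n - 3)) = tanh(2.80 / sqrt(37)) = 0.43.

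Power at n = 40 is 23% for r = 0.2, 47% for r = 0.3, 73% for r = 0.4 and 92% for r = 0.5. If the true correlation were zero, the 95% interval would be about ±0.31, from tanh(1.96 / sqrt(37)).

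For a within-patient slope with patient and time as factors, counting one IOP value per patient and time point:

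- Three time points: residual df = 120 - 40 - 2 - 1 = 77; r = tanh(2.80 / sqrt(76)) = 0.31.
- Four time points: residual df = 160 - 40 - 3 - 1 = 116; r = tanh(2.80 / sqrt(115)) = 0.26.

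These two figures are optimistic. They treat readings 15 minutes apart as independent once patient and time are removed, and they assume complete data. The four-point case also needs a pre-water reading of each autonomic variable; among the baseline assessments section 3.1.2 names only postural blood pressure. Nor are these figures directly comparable with 0.43, because a within-patient slope and a between-patient correlation are different quantities.

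**Step 4. What does a time factor do?** Time as a categorical factor absorbs the average course shared by all patients, leaving only individual deviations. A reflex acting alike in everyone would then leave little in the coefficient. Without the factor, any two variables that both move after water will appear related. Neither version settles the hypothesis alone.

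**The case against.** The strongest reply is that hypothesis 3 is about timing and direction rather than correlation between patients. Section 1.1.2 frames the open question as one of time course, and the lay summary in section 2 aims only to show how blood pressure and heart rate change during the test. On that reading a change-over-time analysis is a reasonable first step, and the shared 15-minute schedule lets the curves be set beside the IOP curve. This stands in part. Comparing timing still requires IOP in the analysis, however, and two curves inspected side by side give no estimate and no interval.

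A reader might infer that the association can never be examined under this plan. The documents do not support that: the list in section 7.4.3 is introduced in open terms, so the accurate statement is that no linking analysis is pre-specified. A reader might also infer that parallel mean changes will be taken as proof of a mechanism. No section says so; the plan gives no decision rule at all.

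It is also fair to say that this is an exploratory secondary aim in a pilot, that the primary comparison is unaffected, and that a within-patient association would not itself prove a reflex. These points limit the weight of the concern. They do not supply the missing link.

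**Conclusion.** The point holds in this form: hypothesis 3 and its rationale concern autonomic changes in relation to the IOP rise, and no pre-specified analysis links an autonomic variable to IOP. The listed analysis can establish that each variable moves after water, but not that the movements are linked within patients or aligned in time. This conclusion rests on setting sections 1.1.2, 1.2, 3.1 and 7.4.3 side by side and depends on none of the assumed values in the calculations.

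It would go too far to conclude that the coefficient from a within-patient model with time as a factor should decide the hypothesis. That model removes the shared time course, which section 1.1.2 treats as the question of interest.

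The gap is worth closing because the readings are already scheduled, but expectations should be modest. About r = 0.43 is detectable with one value per patient, and the within-patient 0.26 to 0.31 is a best case.

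**What to change.** In section 7.4.3, add for hypothesis 3:

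- **Joint time profiles.** Describe IOP and autonomic variables together over the shared 15-minute readings, with onset and peak timing and confidence intervals. Timing can be resolved no more finely than that spacing.
- **A linking model.** Fit a mixed model of IOP on the concurrent autonomic variable, split into within-patient and patient-mean parts, with eye within patient as random effects. Report it with and without categorical time, and say why both are shown. Heart rate and blood pressure are common to both eyes, so the model should also allow for correlation between the two eyes at the same reading.
- **One lead autonomic variable**, named in advance. Treat the others and any lagged versions as exploratory.
- **Conclusion wording.** Give an estimate with its confidence interval, and say beforehand what pattern would count as consistent with a reflex.

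State also when the baseline value of heart rate, saturation and pupil diameter is taken; the change analysis already listed needs it.

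If no linking analysis is added, limit the hypothesis 3 conclusion to a description of autonomic changes after water.

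The cost is SAP wording and analysis time, with no added post-water readings. It is more than one model: four variables, concurrent and lagged, make 4 × 2 = 8, and fitting each with and without time makes 16 fits, all of limited precision at 40 patients. Naming a lead variable keeps that number from turning into a search.

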8. REGULATORY ISSUES

8.1 ETHICS APPROVAL

The Study Coordination Centre has obtained approval from the **xxx** Research Ethics Committee (REC) and Health Regulator Authority (HRA). The study must also receive confirmation of capacity and capability from each participating NHS Trust before accepting participants into the study or any research activity is carried out. The study will be conducted in accordance with the recommendations for physicians involved in research on human subjects adopted by the 18th World Medical Assembly, Helsinki 1964 and later revisions.

8.2 CONSENT

Consent to enter the study must be sought from each participant only after a full explanation has been given, an information leaflet offered and a minimum of 24 hours time allowed for consideration. Signed participant consent should be obtained. The right of the participant to refuse to participate without giving reasons must be respected. After the participant has entered the study the clinician remains free to give alternative treatment to that specified in the protocol at any stage if he/she feels it is in the participant's best interest, but the reasons for doing so should be recorded. In these cases the participants remain within the study for the purposes of follow-up and data analysis. All participants are free to withdraw at any time from the protocol treatment without giving reasons and without prejudicing further treatment.

8.3 CONFIDENTIALITY

The Chief Investigator will preserve the confidentiality of participants taking part in the study and is registered under the Data Protection Act.

8.4 INDEMNITY

Imperial College London holds negligent harm and non-negligent harm insurance policies which apply to this study.

8.5 SPONSOR

Imperial College London will act as the main Sponsor for this study. Delegated responsibilities will be assigned to the NHS trusts taking part in this study.

8.6 FUNDING

This study is not funded. Participants will not receive any payments, reimbursement of expenses or any other incentives for taking part in this research.

No payments will be made to investigators not any members of the research team.

8.7 AUDITS

The study may be subject to inspection and audit by Imperial College London under their remit as sponsor and other regulatory bodies to ensure adherence to GCP and the UK Policy Frame Work for Health and Social Care Research.

10. PUBLICATION POLICY

The study results will be published in peer reviewed scientific journals and presented at conferences. Participants' anonymity will be fully respected as no identifiable information will be used in any of the publications or presentations. As stated in the participant information sheet, participants who express interest in finding out about the results will be contacted once the results are made available

